The disease is spread through the ingestion of contaminated food and water. *S. enterica* Typhi and *S. enterica* ser. Paratyphi A are highly invasive and adapted to avoid the innate immune system. Once ingested, the bacteria pass through the intestinal mucosa, mainly of the distal ileum. The bacteria have specialised fimbriae that adhere to the epithelium over the lymphoid tissue of the Peyer's patches in the ileum. The bacteria are taken up by the macrophages and pass into the lymphatic system and then induce their host macrophages to attract more macrophages to the gut-associated lymphoid tissue (GALT). The *Salmonella* reproduce within the macrophages, as they are carried through the mesenteric lymph nodes to the thoracic duct and the lymphatics, and then through to the reticuloendothelial tissues of the liver, spleen, bone marrow and lymph nodes. Once in the reticuloendothelial system, multiplication continues over a period of 8 to 14 days until apoptosis of the macrophages results in a bacteraemia and systemic spread. The bacteria then infect the gallbladder via either bacteraemia or direct extension of infected bile. The result is that the organism re-enters the gastrointestinal tract in the bile and re-infects Peyer patches. Bacteria that do not re-infect the host are typically shed in the stool and are then available to infect other hosts.

the widespread use of antibiotics in developing countries is leading to the development of resistance in typhoidal serovars. Hence, there is a need for a vaccine to protect patients against antibiotic resistant strains of bacteria^[7].

ZH9 has previously been administered to humans at a maximum dose of 1.7×10^{10} CFU and been shown to be well tolerated and immunogenic. It is anticipated that a similar dose of ZH9PA will be required. It is intended that the vaccine contains equal amounts of ZH9 and ZH9PA and therefore, this study will explore two dose levels of ZH9PA and a single dose level of ZH9 plus ZH9PA given in combination. Previous work with ZH9 has identified that a single dose does not give optimal protection against a typhoid challenge strain but it was demonstrated a single dose provided a significant reduction in the microbiological burden of infection and alteration of the clinical disease profiles^[12]. Hence, the safety and immunogenicity of three doses, administered 3 weeks apart will be investigated in this study.

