Each cohort will start with a sentinel group that will consist of 2 participants, 1 will receive placebo and 1 will receive the relevant vaccine for that cohort. No further participants will be dosed until 24 hours after the second participant has received his/her dose. The rest of the cohort will be dosed provided there are no safety issues identified by the Investigator. This design allows maintenance of the “blind” until Day 70.

The clinical phase is anticipated to take place in Q4 2019 and Q2 2020. The end of the study is defined as last participant last visit.

The study will take place in the Clinical Pharmacology Unit of Simbec-Orion (Clinical Unit) under full medical and nursing supervision.

A schedule of all study assessments is provided in [Table 10.7.1](#).

Screening (Day -28 to Day -1)

Screening assessments will be performed from Day -28 to Day -1 to ensure the eligibility of participants. Assessments will be performed as per [Table 10.7.1](#).

Treatment Period (Day 0 to Day 84)

Participants will be admitted to the Clinical Unit on the morning of Day 0 with confirmation of eligibility and baseline assessments performed as per [Table 10.7.1](#). Following a 90 minute (min) fast prior to dose administration, participants will receive the first dose on Day 0, and then continue to fast for a further 90 mins post dose administration; water will be allowed. Following the completion of the 4h post-dose assessments and at the discretion of the Investigator, the participants will be discharged from the Clinical Unit. Participants will return to the Clinical Unit on Day 3 for safety assessments as per [Table 10.7.1](#). For the 7 days following the first dosing visit (Day 1 to Day 7) participants will be required to record their body temperature at home twice a day i.e. once in the morning and once in the evening (a thermometer and a diary will be provided to record body temperature). Participants will return to the Clinical Unit on Day 7 with the diary and to give a blood sample for the peripheral blood mononuclear cells (PBMC)/ALS assay; assessments will be performed as per [Table 10.7.1](#). Participants will return to the Clinical Unit on Day 14 for safety assessments; assessments will be performed as per [Table 10.7.1](#).

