10.2 Dose Escalation Procedures and Stopping Criteria

10.2.1 Dose Escalation Procedures

For each cohort, a summary of all relevant safety (AEs, laboratory safety tests, ECG, vital signs, subject recorded body temperature, concomitant medications) data (up to 7 days post-first dose) will be produced on behalf of the Principal Investigator. Planned doses may be modified following a review of emerging data. Progression to the next dose level and dose selection will be based on the available safety data from all participants for Cohort 1 prior to dosing Cohort 2 and a minimum of 14 participants¹ for Cohort 2 prior to dosing Cohort 3. Dose escalation will be dependent upon the accrual of acceptable safety data. If it is not appropriate to escalate the dose according to the proposed dose escalation schedule, then the same dose, an intermediate dose or a lower dose may be given following discussion between the Sponsor and the Principal Investigator (or deputy).

There will be a Telephone Conference at a pre-appointed time to involve the Simbec-Orion Project Manager and Principal Investigator (or deputy) and the Sponsor's representative(s), including the Sponsor's Responsible Physician. After discussion of all the data, the decision will be made whether to dose escalate and a written document (dose escalation approval form) signed by the Principal Investigator (or deputy) and Sponsor will be produced ratifying that decision. Full minutes, to be agreed by all parties, will be produced for each discussion regarding dose escalation and filed in the Investigator Site File (ISF). A copy of the signed dose escalation approval form will be provided to the Simbec-Orion Pharmacist and this will allow the IMP to be assembled for the next dose level.

Dose escalation stopping criteria are detailed in [Section 10.2.2.2](#).

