10.3 Discussion of Study Design, including the Choice of Control Groups

This is a Phase I, first in human, randomised, double-blind, placebo-controlled, parallel group, study. Randomised, double-blind studies are the gold standard methodology to assess the safety, tolerability and efficacy of products and therefore, this design has been used for this study. In the case of this study, it will remain fully blinded until Day 70, when a stool sample is taken to assess if participants are shedding the bacterial strains of the vaccine in their faeces. The Investigators and the Monitor will be unblinded to the treatment allocation of participants who have a positive result for *Salmonella* and the participant will receive a course of antibiotics.

No benefit to participants is expected, as efficacy has not been evaluated for the ZH9/ZH9PA combination or for ZH9PA on its own; therefore, use of placebo as the control is considered acceptable in the healthy participants participating in the study. The use of the placebo control allows an assessment of the immune response and provides a background incidence of adverse events.

Previous work with ZH9 has shown that the double mutation does appropriately attenuate the bacteria, however it is known that the bacterial strains that make up the vaccine can be shed in the stools of participants. The vaccine strains are genetically modified organisms, and as such it is necessary to reduce environmental exposure and stool cultures are taken to ensure that participants are not shedding.

There remains a theoretical risk of the vaccine strains causing a systemic infection and so body temperatures will be taken for 7 days post each dose of vaccine. The vaccine strains are

sensitive to several antibiotics, which can be used to treat an infection in the unlikely event such an event occurs.

Three doses are to be studied, as vaccines usually require more than one dose to induce a robust immune response.

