Concomitant Medication	X	X	X	X	X	X	X	X	X	X	X	X	X	X	X

Study Flow Chart Footnotes:

All procedures on dosing days (Days 0, 21, 42) are to be completed prior to dosing (except post dosing vital signs and health check for discharge)

¹ The treatment period will be approximately 85 days duration, from the first dosing day (Day 0) until Day 84 (inclusive).

² Post-study follow-up telephone call will be performed on Days 154 and 224 after receiving the first dose of IMP (Day 0).

³ Eligibility will be confirmed prior to dose administration on Day 0, Day 21 and Day 42.

⁴ For female participants only.

⁵ For postmenopausal female participants only

⁶ At Day 0, Day 21, and Day 42, vital signs to be performed pre-dose and at 4 hours post-dose.

⁷ IMP will be administered fasted (90 mins prior to dose administration). Participants will fast for a further 90 mins post each dose administration. Participants in sentinel cohorts will be contacted by telephone approximately 24 hours following the Day 0 dose to assess their safety profile.

⁸ Participants to record body temperature twice daily at home for 7 days post administration of each dose of IMP.

⁹ Blood cultures to be performed to identify vaccine strains only if a participant experiences defined symptoms (e.g., fever greater than 37.8°C, white blood cell (WBC) >20x10⁹ cells/L, respiratory rate >25 breaths per min, pulse rate >130 beats per min (bpm)) or clinically indicated.

¹⁰ Participants will attend the Clinical Unit on Day 70 to provide a stool sample. If the stool sample is positive for any *Salmonella* strain at Day 70, it will be presumed to be one of the vaccine strains, and participants will be asked to return to the Clinical Unit to receive a course of antibiotic therapy, and a repeat stool culture will be obtained on Day 84 to confirm shedding of *Salmonella*, presumed to be one of the vaccine strains, has ceased.

¹¹ Samples to be collected prior to each dosing.

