10.9.1.1 Study Variables/Endpoints

Primary Endpoint

- Local and systemic reactogenicity up to Day 84 as assessed by adverse events, laboratory safety tests (biochemistry, haematology, urinalysis), vital signs and physical examination.

Secondary Endpoints

- Local and systemic reactogenicity; from Day 85 to Day 224 as assessed by adverse events, laboratory safety tests (biochemistry, haematology, urinalysis) if undertaken for cause; vital signs if undertaken for cause; physical exam if undertaken for cause.
- Concentrations of specific serum IgA and IgG antibodies to LPS O:2 and O:9, flagellin H:a and H:d.
- Fold increase in specific serum IgA and IgG antibody concentrations, in individual participants, against the antigens LPS O:2 and O:9, flagellin H:a and H:d.
- Concentrations of specific mucosal IgA antibodies in lymphocyte supernatant (ALS) assays, in individual participants, against antigens LPS O:2 and O:9, flagellin H:a and H:d.
- Seroconversion rate (proportion of participants with 4-fold increase above baseline at any time post vaccination) against each of the above antigens.
- Fold increase in specific mucosal IgA antibodies in lymphocyte supernatant (ALS) assays, in individual participants, against the antigens LPS O:2 and O:9, flagellin H:a and H:d.

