10.9.1.3.3 Safety Data

All safety data will be listed, in addition:

AEs: All AEs will be coded using the Medical Dictionary for Regulatory Activities (MedDRA) dictionary (the most up to date version will be used and this will be documented in the DMP)

All AEs, including those which occurred prior to receiving the first dose of IMP, will be listed. Only treatment emergent adverse events (TEAEs), i.e., existing conditions that worsen or events that occur during the course of the study after administration of IMP, will be included within the summary tables. AE summaries will be presented by treatment, all active treatments combined and overall.

An overall summary of AEs will be produced including the number of TEAEs; the number and % of participants reporting at least 1 TEAE, serious TEAE, TEAE leading to withdrawal from the study; the number and % of participants reporting TEAEs by severity and relationship to IMP.

The number of TEAEs and the number and % of participants reporting at least 1 TEAE will be tabulated by system organ class (SOC) and preferred term. A participant reporting multiple episodes of a particular AE will only contribute 1 count towards the corresponding SOC and preferred term.

The number of TEAEs and the number and % of participants reporting at least 1 TEAE will be tabulated by preferred term and sorted by descending frequency on the total number of participants with that AE. A participant reporting multiple episodes of a particular AE within a treatment period will only contribute 1 count towards the corresponding preferred term.

In addition, the number and % of participants reporting TEAEs will be tabulated by maximum severity and strongest relationship to IMP. For the summary of TEAEs by severity, if a participant has multiple events occurring within the same SOC or preferred term the event with the highest severity will be counted. Similarly, for TEAEs by relationship to IMP, if a participant has multiple events occurring within the same SOC or preferred term, the event with the highest association to IMP will be counted.

The incidence of TEAEs will be compared between treatments using Fisher's Exact Test (or an alternative statistical test if appropriate).

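### The primary endpoint is reactogenicity, but the post-dose diary is described for temperature only, and diary temperature has no specified final table

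*Combined protocol and SAP*

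**What the plan says.** - **Endpoint (Section 10.9.1.1).** The primary endpoint is "Local and systemic reactogenicity up to Day 84 as assessed by adverse events, laboratory safety tests (biochemistry, haematology, urinalysis), vital signs and physical examination".
- **Diary (Section 10.1 and Table 10.7.1, footnote 8).** After each dose, "a thermometer and a diary will be provided to record body temperature". The footnote gives the frequency: "Participants to record body temperature twice daily at home for 7 days post administration of each dose of IMP". No other diary field is described.
- **Adverse events (Section 10.7.1.3.1).** All events are recorded from consent onward, with onset and resolution times. The Investigator assigns one of three general severity grades, based on interference with daily routine or on objective change. There is no list of solicited symptoms and no statement of how events are elicited.
- **Contacts.** Visits fall 3 and 7 days after each dose, with a further visit at Day 14 after the first dose. Vital signs are repeated 4 hours after each dose. The two dose leaders in each cohort also get a telephone call about 24 hours after their first dose (Section 10.6.8).
- **Use of diary temperature.** The cohort safety summary in Section 10.2.1 covers "AEs, laboratory safety tests, ECG, vital signs, subject recorded body temperature, concomitant medications) data (up to 7 days post-first dose". Section 10.9.1.3.3 opens with a general rule, "All safety data will be listed, in addition", and then specifies tables for treatment-emergent events and descriptive statistics for laboratory values and vital signs. Diary temperature is not named there.
- **Analysis sets (Section 10.9.1.2).** Vomiting or diarrhoea that could affect exposure to the product removes a participant from the Per Protocol Set.
- **SAP (Section 10.9.1).** A separate SAP is to be written before database lock.

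**The concern.** An endpoint called reactogenicity is normally measured by asking every participant, every day, about a fixed list of expected reactions. For a live oral bacterial vaccine, the reactions of interest are mainly gut symptoms and general systemic symptoms in the days after each dose. This plan prompts for none of them. It issues and collects a diary after every dose but describes it for temperature alone.

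Two things are at stake. First, mild, short-lived reactions may go unreported, which would understate rates in every group and, if capture is similar across groups, shrink the absolute vaccine-placebo difference. Second, the temperature record that is collected has no specified place in the final tables, although persistent fever is both a dose-escalation criterion (Section 10.2.2.2) and an individual criterion (Section 10.5.5). The Per Protocol rule adds to the first problem, because membership turns partly on vomiting and diarrhoea for which no daily record is described.

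**Working it through.** The plan gives no capture rate, expected reaction rate or power figure, so there is no stated number to reproduce. The check is mainly a comparison of what the endpoint needs with what is collected and tabulated.

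**1. Which endpoint source can hold a gut or general symptom?**
- Laboratory tests: no.
- Vital signs: temperature, pulse and blood pressure only.
- Physical examination: scheduled at Screening and Day 84 (Table 10.7.1), so not in the week after a dose.
- Adverse events: yes, and this is the only source that can.

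**2. Gaps between scheduled contacts (Table 10.7.1, nominal days).**
- First week after each dose: 3 − 0 = 3 days, then 7 − 3 = 4 days. With the ±1 day windows these can reach 4 and 6 days.
- After that, dose 1: 7 and 7 days (Days 7, 14, 21).
- Dose 2: 42 − 28 = 14 days.
- Dose 3: 70 − 49 = 21 days, then 84 − 70 = 14 days.

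**3. Volume of diary temperature.**
- Per participant: 2 readings × 7 days × 3 doses = 42.
- All participants: 42 × 45 = 1,890, if all take three doses and complete the diary.
- Within the first-dose review window of Section 10.2.1: at most 2 × 7 × 45 = 630.
- After doses 2 and 3, with no review summary specified: 1,890 − 630 = 1,260.
- With a specified final table: none. All fall under the general listing rule.

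**4. What incomplete capture would do (illustration only).** Let p be the true reaction rate and s the share of reactions recorded. Both are assumptions. The chance of recording at least one case among n vaccinees is 1 − (1 − s·p)^n. With n = 12, the number on vaccine in Cohorts 2 and 3:

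| True rate p | s = 100% | s = 75% | s = 50% |
|---|---|---|---|
| 10% | 72% | 61% | 46% |
| 20% | 93% | 86% | 72% |

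For example, 1 − 0.90^12 = 0.718 and 1 − 0.95^12 = 0.460.

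If s is the same in both groups, the risk difference is multiplied by s and the risk ratio does not change. An assumed 50% versus 20% would be seen as 25% versus 10% at s = 50%, a difference of 15 points instead of 30, with the ratio still 2.5.

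**5. Precision even with full capture.** With 0 of 12 affected, the exact two-sided 95% upper limit is 1 − 0.025^(1/12) = 26.5%. A recorded zero is weak evidence at this size, so intervals belong beside the percentages.

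**The case against.** The strongest reply is that the plan already captures these reactions. All adverse events are recorded however minor, with onset and resolution times, and the first-week visits keep nominal gaps to 3 or 4 days. Doses are taken under supervision, with a 4-hour check afterwards, and the dose leaders are called the next day. The Per Protocol rule covers only vomiting or diarrhoea that could affect exposure, and events soon after dosing may well be seen in the unit. The diary form and site procedures are not supplied, and a SAP is still to come.

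Much of this stands. Because the plan does not say how events are elicited, dependence on recall is an inference, and the capture rate is unknown. But a SAP can only add tables. It cannot recover symptoms that nobody was asked about.

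Several stronger readings are tempting but not supported:
- **Diary temperature is never used.** Section 10.2.1 names it in the first-dose safety summary, and Section 10.9.1.3.3 lists all safety data.
- **Fever has no between-group summary.** Fever reported as an adverse event enters the tables by treatment, and event incidence is compared with Fisher's exact test. Clinic oral temperature is summarised by treatment and time-point. Only the diary readings lack a table.
- **Severity is graded inconsistently.** One three-level scale, applied by an Investigator with one grade per event, is mandatory. It is general rather than symptom-specific, but nothing shows inconsistency.
- **The 7-day window contradicts Section 8.** Section 10.3 says "There remains a theoretical risk of the vaccine strains causing a systemic infection and so body temperatures will be taken for 7 days", while Section 8 says "multiplication continues over a period of 8 to 14 days until apoptosis of the macrophages results in a bacteraemia and systemic spread". The second statement describes natural infection with typhoidal serovars. Section 10.3 describes the vaccine strains as attenuated, and the documents never apply the 8 to 14 day interval to them.

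**Conclusion.** The point holds as a cheap improvement to the measurement of the primary endpoint. Two facts rest on the text alone. No solicited gut or systemic symptom record is described for an endpoint defined as reactogenicity. And no final tabulation of diary temperature, nor any review summary of it after doses 2 and 3, is specified.

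Under-capture of short-lived reactions is a likely consequence of the first, but its size cannot be derived from the documents. The figures in step 4 show only how sensitive a group of 12 would be under assumed rates. A reader might take them as an estimate of lost events or lost power, and they are neither. Section 10.9.2 states that the sample size has no formal statistical basis, so there is no planned power to lose.

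**What to change.** 1. **Collection.** Add to the existing diary a daily checklist of gut and systemic symptoms with a severity grade, for the same 7 days after each of the three doses. The sponsor and the investigator should choose the symptoms. State in Section 10.7.1.3.1 how other adverse events are elicited at visits.
2. **Analysis.** Prespecify one table by dose and treatment giving the number and percentage of participants with any and with severe solicited reactions, the maximum diary temperature, and the proportion above the protocol's existing fever cut-offs, with exact 95% confidence intervals for proportions. Section 10.2.2.2 sets its febrile criterion above 38.5°C and Section 10.5.5 at or above 38.5°C. These passages must be reconciled before the table is programmed.
3. **Per Protocol Set.** Name the checklist, together with adverse events, as the source for the vomiting and diarrhoea rule in Section 10.9.1.2.

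**Cost.** One diary page, one eCRF form and one table, with no new visit. Participants carry slightly more burden, and reported reaction rates will rise in all groups, placebo included. Changing how a primary endpoint is collected needs a protocol amendment, which may count as substantial under Section 11.2. The collection change has to come before dosing. If dosing has begun, the temperature table can still be added through the SAP, and the report should say that reactogenicity rests on adverse events without a solicited symptom record.

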10.2 Dose Escalation Procedures and Stopping Criteria

10.2.1 Dose Escalation Procedures

For each cohort, a summary of all relevant safety (AEs, laboratory safety tests, ECG, vital signs, subject recorded body temperature, concomitant medications) data (up to 7 days post-first dose) will be produced on behalf of the Principal Investigator. Planned doses may be modified following a review of emerging data. Progression to the next dose level and dose selection will be based on the available safety data from all participants for Cohort 1 prior to dosing Cohort 2 and a minimum of 14 participants¹ for Cohort 2 prior to dosing Cohort 3. Dose escalation will be dependent upon the accrual of acceptable safety data. If it is not appropriate to escalate the dose according to the proposed dose escalation schedule, then the same dose, an intermediate dose or a lower dose may be given following discussion between the Sponsor and the Principal Investigator (or deputy).

There will be a Telephone Conference at a pre-appointed time to involve the Simbec-Orion Project Manager and Principal Investigator (or deputy) and the Sponsor's representative(s), including the Sponsor's Responsible Physician. After discussion of all the data, the decision will be made whether to dose escalate and a written document (dose escalation approval form) signed by the Principal Investigator (or deputy) and Sponsor will be produced ratifying that decision. Full minutes, to be agreed by all parties, will be produced for each discussion regarding dose escalation and filed in the Investigator Site File (ISF). A copy of the signed dose escalation approval form will be provided to the Simbec-Orion Pharmacist and this will allow the IMP to be assembled for the next dose level.

Dose escalation stopping criteria are detailed in [Section 10.2.2.2](#).

